#### 5.2.8 Study Drug Exposure and Compliance

For each patient, the length of exposure to study drug will be calculated as the number of days from the first dose of study drug to the last dose of study drug, regardless if the patient missed one or more doses of study drug. Length of exposure will be summarized by previous treatment group in parent study and overall in OLE study using descriptive statistics for the safety population.

For each patient, overall compliance (%) will be calculated as: (Total Number of Tablets Dispensed – Total Number of Tablets Returned)\*100/ (Treatment Duration in Days). The number and percentage of patients who were compliant with taking study drug will be summarized by previous treatment group in parent study and overall in OLE study for the safety population for the following categories  $0 - \langle 80\% \rangle \geq 80\%$ .

The study drug administration and compliance data will be listed for each patient.

Confidential

Page 14 of 27

## 5.3 Efficacy Endpoints and Analyses

Given the primary objective of the study being long term safety, efficacy analyses will be using the safety population (SP). The efficacy data will be summarized by previous treatment group in parent study as well as an overall group.

For each efficacy parameter, descriptive summary statistics at each visit will be provided for the observed value, change from baseline, and percent change from baseline in both conventional and International System of Units (SI). Two sets of summaries will be provided using the baseline from the parent study and from the OLE study. The visits to be included in the overtime summary are baseline of parent study (1002-040), baseline of OLE study, week 12, week 52, week 78, and Week 82. There will be no imputation for missing data, all summaries will use the observed data. Ninety-five percent (95%) CI will be provided for the estimates at post-baseline visits.

In addition, efficacy parameters will also be summarized using the Completer Analysis Set (CAS).

For LDL-C, the same descriptive summary statistics at each scheduled visit will be provided within each subgroup for the observed value, change from baseline, and percent change from baseline.

Efficacy data (observed value, change from baseline, and percent change from baseline) from all visits will be summarized using descriptive statistics in both conventional and standard units.

Figures (mean  $\pm$  standard deviation or median/interquartile range) supporting the summary tables will be provided for each efficacy parameter.

Efficacy data from all visits will be provided in listings as well.

By-visit summary for efficacy endpoints (LDL-C, non-HDL-C, TC, HDL-C, TG, ApoB, and hs-CRP,) using the CAS will be provided in conventional and standard units.

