Patient incidence of adverse events (AEs)

Secondary Endpoints:

- Percent change from baseline in LDL-C at Weeks 52 and 78
- Change from baseline in LDL-C at Weeks 52 and 78
- Percent change from baseline in non-HDL-C at Weeks 52 and 78
- Percent change from baseline in TC at Weeks 52 and 78
- Percent change from baseline in ApoB at Weeks 52 and 78
- Percent change from baseline in hs-CRP at Weeks 52 and 78
- Percent change from baseline in TG at Weeks 52 and 78
- Percent change from baseline in HDL-C at Weeks 52 and 78

Number of patients (planned): The number of patients entering this study will depend on the number of patients completing Study 1002-040 and their willingness to enroll and continue taking investigational product. Approximately 1300 patients of the 1950 eligible from parent study 1002-040 are expected to participate in this study.

Diagnosis and Criteria for Inclusion:

Key inclusion criteria

- 1. Successfully completed the parent study (1002-040) and meet both of the following criteria:
 - The patient was compliant with the parent study requirements including study visits, procedures, and investigational medicinal product (IMP) in the opinion of the principal investigator;
 - The patient was able to tolerate IMP through the end of the parent study.

Key exclusion criteria

- 1. Female patient is not willing to use at least 1 acceptable method of birth control during treatment and for an additional 30 days after the end of treatment unless patient is sterilized or postmenopausal;
 - Menopause is defined as greater than 55 years and ≥1 year without menses, less than 55 years and ≥1 year without menses with follicle-stimulating hormone (FSH) ≥40.0 IU/L, or surgically sterile (including hysterectomy and/or bilateral oophorectomy);
 - Acceptable methods of birth control include: oral birth control medications; placement of an intrauterine device (IUD) with or without hormones; barrier methods including condom or occlusive cap with spermicidal foam or spermicidal jelly; vasectomized male partner who is the sole partner for this patient; or true abstinence where it is the preferred and usual lifestyle of the patient (not including periodic abstinence such as calendar, ovulation, symptothermal, postovulation methods, or withdrawal).

- 2. Patient is pregnant or breast feeding, or might become pregnant during treatment and/or within 30 days after the end of treatment

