9.2.4. Month 12 (Week 52 ±7 days)

If the patient is withdrawing early from the study at this visit, proceed to Section 9.3.2 for the list of the required assessments.

If the patient is withdrawing from IMP treatment at this visit, proceed to Section 9.3.2 for the list of the required assessments. The patient will be asked to continue to be followed for safety using the protocol-specified visit schedule. If the patient consents for follow-up, schedule the next protocol-specified visit.

Patients who do not provide consent to continue to return to the clinic for safety assessments after withdrawing from IMP treatment will be asked to participate in phone calls from the site at protocol-specified visits, or at a minimum at 78 weeks, to inquire about the patient's current health status and collect information on AEs (eg, recent procedures, hospitalizations, and if the patient has died, the cause of death). If the patient consents for telephone contacts, schedule the next protocol-specified visit.

Patients will undergo the following assessments and procedures:

- Concomitant medication review (ongoing)
- Assess AEs, SAEs, and potential clinical endpoints
- Weight
- Vital signs
- Physical Exam
- Clinical laboratory evaluations:
 - Hematology, blood chemistry, and urinalysis
 - Basic fasting lipids (TC, calculated LDL C, HDL C, non-HDL C, and TG)
 - ApoB and hs-CRP
 - HbA_{1C}
- Return of IMP; assessment and recording of IMP compliance
- Dispense IMP containers to patient for continued dosing and provide dosing instruction
- Schedule next visit

Note: If this visit is being conducted at the site for patients who have consented to be followed for safety assessments, including basic fasting lipids, after withdrawing from IMP treatment, all assessments except for those procedures pertaining to IMP management (IMP dispensing, IMP compliance, IMP accountability) should be completed.

Note: If this visit is being conducted by telephone contact for patients who have consented to be followed by phone for safety assessments after withdrawing from IMP treatment, collect information as reported by the patient regarding AEs, concomitant medication, and current health status.

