9.3. Patient Withdrawal Criteria

9.3.1. Early Withdrawal from the Study

Patients must remain in the study until the last scheduled visit at Month 19 (Week 82) to be considered as having completed participation in the study. Patients must remain in the study through Month 18 (Week 78) to be considered as having completed participation in the treatment portion of the study.

Patients who withdraw from IMP prior to Month 18 (Week 78) for any reason will be asked to continue to be followed for safety assessments, including basic fasting lipids, at clinic visit following the protocol-specified visit schedule (see Appendix 1). The patient must provide consent to be followed in the study after withdrawing from IMP treatment. Protocol procedures to be completed for patients who consent will include those specified at each visit as noted in Schedule of Events (see Appendix 1).

Patients who temporarily withdraw from IMP prior to Month 18 (Week 78) for any reason may restart IMP providing that 1) the patient and the investigator are in agreement regarding this course of action, and 2) IMP can be started as soon as possible. For cases where the patient has been off of IMP for more than 4 weeks, the investigator must contact the medical monitor for approval prior to restarting IMP.

Patients who do not provide consent to continue to return to the clinic for safety assessments will be asked to participate in phone calls from the site at protocol-specified visits (see Appendix 1), or at a minimum at 78 weeks, to collect information on AEs, concomitant medications, and current health status. The patient must provide consent to be contacted by phone by site personnel for the purposes of assessing current AEs and current health status.

The patient's decision to participate in the clinical study is voluntary. Patients may refuse to continue in the study and/or withdraw from participation in this study at any time, for any reason, specified or unspecified, and without penalty or loss of benefits to which the patient is otherwise entitled.

It is the right and duty of the Investigator to interrupt the treatment of any patient whose health or well-being may be threatened by continuation in this study. Such patients should be withdrawn from the study and should not be continued under a modified regimen.

Patients who are withdrawn from the study may not re-enter. The reasons for withdrawal from this study may include:

- Unacceptable AE
- Patient's withdrawal of consent

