12. STATISTICS

12.1. General Considerations

Statistical analyses in this open label, multicenter single arm study will be descriptive in nature. No statistical inference is planned. Patient disposition, demographics and baseline characteristics will be summarized. Summary statistics for continuous variables will include the number of patients, mean, median, standard deviation or standard error, first and third quartiles minimum, and maximum. For categorical variables, the frequency and percentage will be given. Ninety-five percent (95%) confidence intervals (CIs) will be calculated for select continuous and categorical endpoint estimates. All patients will be summarized together as well as by their prior treatment group in the parent study.

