### 5.4.5 Laboratory Evaluations

Two sets of baseline for safety parameters are defined, similar to that for the efficacy parameters, baseline from the parent study and the baseline from the OLE study.

Continuous laboratory parameters (serum chemistry, hematology, coagulation (only for those patients receiving anti-coagulation), urinalysis, urinalysis [microscopic]) listed in Table 4 will be summarized using descriptive statistics at each scheduled visit starting from the baseline of the parent study. The similar on-treatment and completer analysis set approach for efficacy analysis described in section 5.3 will be used for safety laboratory analysis. All analysis will use conventional unit and SI unit will be provided for selected parameters.

Fasting serum glucose and HbA1c will be summarized using descriptive statistics for the observed value and the change, percent change from baseline by history of diabetics. Missing values for any of the laboratory evaluations will not be imputed; that is, only observed case data will be used.

Confidential

Page 18 of 27

Page 70 of 129

Version 1.2, Dec 05, 2018 Statistical Analysis Plan

Categorical urinalysis data will be listed, but will not be summarized.

As part of the AESI evaluation, below safety lab abnormality will be summarized by treatment group. All post-baseline lab values during the on-treatment period are being considered. Further details are provided in Section 5.4.6.1 through 5.4.6.4.

- ALT or AST (>  $3 \times$  ULN and > $5 \times$  ULN)
- TB (>  $2 \times ULN$ )
- Potential Hy's Law case: (ALT and/or AST > 3 × ULN with concurrent TB > 2 × ULN)
- CK (>  $5 \times ULN$ ) and (> $10 \times ULN$ )
- Fasting Serum Glucose (mg/dL) ( $\leq$  50, and  $\geq$  126) by history of diabetics
- HbA1C ( $\geq 6.5\%$ ) by history of diabetics
- Creatinine (change from baseline for >1 mg/dL)
- eGFR (< 15 mL/min/1.73m^2, 15 29 mL/min/1.73m^2)
- Hgb (g/dL) (decrease from baseline for  $\geq 2$  g/dL)
- Hgb (< 8 g/dL)

The number and percentage of patients with the following laboratory abnormalities will be summarized by the parent study baseline statin intensity, previous treatment group in the parent study, and overall in the OLE study:

- ALT or AST (>  $3 \times$  ULN and > $5 \times$  ULN)
- TB (>  $2 \times ULN$ )
- Potential Hy's Law case: (ALT and/or AST >  $3 \times$  ULN with concurrent TB >  $2 \times$  ULN)
- CK (>  $5 \times$  ULN) and (> $10 \times$  ULN)

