# **3** Study Objectives and Endpoints

## 3.1 Objectives

- The primary objective for this study is to characterize the safety and tolerability of long-term administration of bempedoic acid (ETC-1002) 180 mg
- The secondary objective is to characterize the efficacy of long-term administration of bempedoic acid 180 mg/day as assessed by changes in low-density lipoprotein cholesterol (LDL-C), high-density lipoprotein cholesterol (HDL-C), non-high-density lipoprotein cholesterol (non-HDL-C), apolipoprotein B (ApoB), total cholesterol (TC), triglycerides TG, and high-sensitivity C-reactive protein (hs-CRP) in patients with hyperlipidemia

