#### 5.2.7 Concomitant Medications

Concomitant medications are defined as medications that were ongoing at the time of study drug initiation in this OLE study or new medications that started post study drug initiation and within 30 days following the date of the last dose of study drug.

Medications, including lipid modifying therapy (LMT) medications, will be coded using WHO Drug (March, 2017, or later if appropriate). The frequency of use of concomitant medications will be summarized by previous treatment group in parent study, as well as overall in OLE study, for the safety population according to Anatomical Therapeutic Chemical (ATC) class and preferred term. Concomitant medications will be listed for each patient. Concomitant LMT medications will be summarized by ATC class and medication name and listed separately in a similar fashion.

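### SAP 5.3 pools on-drug and post-discontinuation lipid values, and no planned table shows all patients on bempedoic acid at Week 52 or counts off-drug values by visit

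*SAP*

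**What the plan says.** **Objective.** SAP v1.3 section 3.1: "The secondary objective is to characterize the efficacy of long-term administration of bempedoic acid 180 mg/day". The secondary endpoints are lipid and hs-CRP changes at Weeks 52 and 78.

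**Data collected after stopping.** Under Protocol 9.3.1, patients who withdraw from study drug before Week 78 "will be asked to continue to be followed for safety assessments, including basic fasting lipids, at clinic visit following the protocol-specified visit schedule". The Week 52 visit note (Protocol 9.2.4) covers patients "who have consented to be followed for safety assessments, including basic fasting lipids, after withdrawing from IMP treatment" and omits only the drug-management procedures. The Week 12 note says the same. Follow-up needs consent: some stoppers will be followed by phone only, and others will have early end-of-treatment and end-of-study visits and nothing more.

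**Analysis.** SAP 5.3 uses the Safety Population (at least one extension dose): "There will be no imputation for missing data, all summaries will use the observed data". It also plans every efficacy parameter by visit in the Completer Analysis Set (CAS), meaning patients who completed 78 weeks of treatment. It has no rule to separate, flag or count values drawn after the last dose.

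**Background therapy.** Protocol 10.1.4.4.1 unmasks lipids after Week 12 and then allows concomitant medication to be adjusted. SAP 5.2.7 counts as concomitant those drugs ongoing at first dose and "new medications that started post study drug initiation and within 30 days following the date of the last dose of study drug".

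**The concern.** A scheduled Week 52 or 78 sample from someone who stopped months earlier measures no drug effect, or the effect of whatever replaced the drug. In the main summary it carries the same weight as a sample from a patient still taking bempedoic acid. The point concerns correctly timed scheduled visits of patients who have stopped. Early-withdrawal visits that fall into a nearby analysis window are a separate matter.

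The SAP draws this line elsewhere. Treatment-emergent adverse events end 30 days after last dose (3.2.1), and the laboratory abnormalities of special interest use an on-treatment period (5.4.4), though that period is not defined. Efficacy has no equivalent.

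At stake is how the long-term lipid results are read. A reader who takes the Week 52 mean and its interval as the effect of staying on drug could be wrong by an unknown amount. The lipid-therapy table that might explain a shift can miss the relevant drugs.

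**Working it through.** **1. Is there a plan figure to reproduce?** No. Protocol 12.1 states "No statistical inference is planned", and the synopsis gives only an expected rollover: "Approximately 1300 patients of the 1950 eligible from parent study 1002-040 are expected to participate in this study" (1300/1950 = 66.7%). Neither document gives an effect size, SD or discontinuation rate. Every input in steps 3 to 5 is an assumption.

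**2. What each planned summary contains.**

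| Patient | Safety Population | CAS |
|---|---|---|
| On drug through Week 78 | on-drug at both visits | on-drug at both visits |
| Stops between Weeks 52 and 78, keeps attending | Week 52 on-drug, Week 78 off-drug | dropped at both visits |
| Stops before Week 52, keeps attending | off-drug at both visits | dropped at both visits |
| Interrupts, restarts, recorded as completing treatment | included, possibly off drug at sampling | included, possibly off drug at sampling |

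At Week 78 the CAS is close to the set of patients on drug. At Week 52 it is not, because the second row gives valid on-drug values that the CAS discards on the basis of later behaviour.

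**3. Size of the shift.** Let f be the share of observed values that are off-drug, and q the share of those from patients switched to another agent.

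Pooled mean = (1 - f) × on + f × [(1 - q) × off + q × switched]

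Shift = f × [(1 - q) × off + q × switched - on]

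Assume LDL-C change of -15% on drug, 0% off drug and -50% switched. Then shift = f × (15 - 50q) percentage points. A positive shift means a smaller apparent reduction.

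| f | q = 0 | q = 0.3 | q = 0.5 | q = 1 |
|---|---|---|---|---|
| 2% | +0.3 | 0 | -0.2 | -0.7 |
| 10% | +1.5 | 0 | -1.0 | -3.5 |
| 20% | +3.0 | 0 | -2.0 | -7.0 |

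The pooled mean at f = 10% is therefore -13.5% (q = 0) or -18.5% (q = 1); at f = 20% it is -12.0% or -22.0%.

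**4. Against the reported precision.** With SD 25 and n = 1100 (both assumed), the 95% half-width is 1.96 × 25/√1100 = 1.48 points. Pure dilution reaches this at f = 1.48/15 = 9.9%. If all stoppers switch, it is reached at f = 1.48/35 = 4.2%. At f = 2% neither shift reaches it.

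**5. Other inputs.** With on-drug change -10%, -20% or -30% and -40% after new therapy, f = 10% gives +1, +2 or +3 points with no new therapy and -3, -2 or -1 with new therapy in all stoppers. The sign changes at q = 25%, 50% and 75%. The half-width at n = 1300 is 1.09 (SD 20) to 1.63 (SD 30).

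**6. The 30-day limit.** A lipid drug started on day 31 or later after the last dose is outside the SAP 5.2.7 definition, so it is absent from the lipid-modifying-therapy summary built on it. Its effect is still present in any later Week 52 or 78 sample pooled under 5.3.

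**The case against.** **All-observed is a legitimate summary.** It describes lipids under a policy of starting bempedoic acid, whatever followed. It also fits Protocol 12.3 and 12.5, which planned efficacy on all enrolled patients without imputation. This stands. A reader might infer that the endpoints say nothing about long-term administration. The documents do not support that: the summary answers a different question, and the plan should say which one.

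**The CAS already handles Week 78.** Largely true. The Safety Population count minus the CAS count at that visit approximates the number off drug, and comparing the two means shows the direction of the shift. The objection does not reach Week 52.

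**A shift in either direction is not automatic.** Correct. Stopping alone only dilutes. Under the main inputs the sign reverses only if more than 30% of off-drug values come from switched patients, and the figure of -7.0 needs all of them switched and a 20% off-drug share.

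**The off-drug share may be small.** Possible, since only stoppers who consent to clinic visits contribute values. No figure is given either way, which is a reason to report it.

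**Status can be derived from planned outputs.** Disposition reports drug withdrawals by reason, and dosing and lipid data are listed. Status at each sample could be worked out by hand, but no table shows it.

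**Superseded SAP text.** Versions 1.1 and 1.2, section 5.4.5, refer to "The similar on-treatment and completer analysis set approach for efficacy analysis described in section 5.3". A reader might infer that version 1.3 dropped a planned on-treatment efficacy analysis. Section 5.3 of those versions contains none, so version 1.3 only removed a reference that pointed nowhere. It is not a defect in the current plan.

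**Conclusion.** The point holds within limits. The main Week 52 and 78 lipid summary mixes on-drug and post-discontinuation values and does not isolate the effect of continued bempedoic acid. Three gaps remain after the CAS is taken into account: no table of all patients on drug at Week 52, no count of off-drug values by visit, and a lipid-therapy table that omits drugs started more than 30 days after last dose.

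The size is unknown because the off-drug share is not given. Under the assumed inputs it ranges from negligible at a 2% share to twice the interval half-width for dilution at 20% (3.0 against 1.48), and more if most stoppers switch. No hypothesis test or primary safety result depends on it; the consequence is confined to how descriptive secondary endpoints are interpreted.

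**What to change.** Keep the all-observed and CAS summaries, and describe the all-observed one as a treatment-policy summary.

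1. **SAP 5.3:** add an on-treatment summary in the Safety Population, chiefly for Week 52 and also for Weeks 12 and 78. Define on-treatment from dosing records as drawn on or before last dose plus a short margin fixed in the SAP. Exclude samples taken during recorded interruptions longer than that margin. The exclusion is needed because Protocol 9.3.1 allows patients to stop and restart, so a last-dose rule alone would count those samples as on drug.
2. **SAP 5.3:** show at each visit the number of values on and off study drug at sampling.
3. **SAP 5.2.7:** extend the lipid-modifying-therapy table to drugs started at any time up to the patient's last lipid sample.

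The cost is SAP wording and one extra table set, with a somewhat smaller n in the on-treatment rows. Last-dose dates (Protocol 9.3.2) and medication start and stop dates (Protocol 7.2) are already collected. The documents do not state how fully interruption dates are captured, so the exclusion can only be as complete as those records. No patient procedure changes.
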